5.2 Baseline Medical Conditions and Underlying Disease

Unchanged chronic conditions or those related to the underlying disease which are consistent with the disease's natural progression are not AEs and are not to be recorded on the AE page of the CRF unless there is an exacerbation. These medical conditions are to be adequately documented on the medical history and/or signs and symptoms inventory page of the CRF. However, medical conditions present at baseline (Day –1) that worsen in intensity or frequency during the study must be reported and recorded as AEs.

All HSCT transplant patients are critically ill at the time of their transplant. The most common severe adverse events in this population are cardiopulmonary arrest, progressive respiratory failure requiring intubation, life-threatening opportunistic infection, severe veno-occlusive disease (VOD), and graft failure. It is expected that deaths will occur while this trial is ongoing because of the mortality associated with both allogeneic HSCT and the subjects' underlying diseases. The rates of HSCT-related morbidity and mortality are well-established to be significant. All serious adverse events, including those associated with a fatality, will be carefully and thoroughly evaluated by the Principal Investigator both in the context of the subject's specific history and in the context of the overall protocol. If, after any of these events, the DSMB, in consultation with the Investigators, determines that the continuation of the trial is no longer in the best interests of the subjects, the trial will be suspended immediately.

HSCT recipients are likely to have the following adverse events and laboratory abnormalities that are related to their transplant conditioning regimen or the transplant procedure: nausea, anorexia, vomiting, gastrointestinal injury including severe mucositis, epigastric discomfort and increased stool output during and in the two to three weeks after completion of conditioning, fever and neutropenia, opportunistic infection, VOD, fluid and electrolyte imbalance including hypomagnesemia, hypokalemia, hyponatremia, hypocalcemia, hypophosphatemia, blood sugar and lipid abnormalities, renal insufficiency, transaminitis, GvHD and hemorrhagic cystitis. These transplant-related experiences will not be reported as serious adverse events unless the event is life threatening or fatal. However, they will be collected as AEs and noted as not related to the use of study drug where appropriate. On Day –1, a "signs and symptoms inventory" CRF page will be completed prior to initial dosing with opebacan.

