3.3.2 Definition and Management of Dose-limiting Toxicity

A DLT is defined as a toxicity of CTC grade 3 or greater severity (based on CTCAE Version 3.0) that is deemed by the Investigator related to the investigational agent, occurs within 4 weeks of administration, and is confirmed by the Investigator and Sponsor, or by the DSMB. A toxicity of CTC grade 2 that is deemed by the Investigator related to the investigational agent and occurs within 4 weeks of administration may also be reported as a potential DLT if the Investigator considers it a clinically significant safety concern.

Given the long list of expected toxicities experienced by patients undergoing HSCT, careful determination of attribution will be particularly important (see Section 5.2).

Sites must notify the Sponsor within 24 hours of having knowledge of a potential DLT. In cases where it is not clear whether an event should be considered related, the Investigator should discuss the case with the Sponsor's medical monitor. Within 24 hours of notification of a potential DLT, the Sponsor will contact the Investigator to discuss the event and together will confirm if it is a DLT. If it is determined that an AE meets all of the criteria for DLT, the subject will discontinue study drug. After receiving treatment for the toxicity (if necessary), the subject will be closely monitored until the toxicity is resolved to no worse than grade 2 severity (grade 1 if reported toxicity is initially grade 2) or is stabilized, at which point he/she will be removed from the study.

If the Investigator and Sponsor cannot agree on the determination of a DLT, the issue will be escalated to the DSMB and the subject will discontinue study drug. Within 7 days of the Sponsor receiving notification of a potential DLT, the DSMB must convene (most likely by teleconference) to determine whether the event is to be classified as a DLT. After receiving treatment for the toxicity (if necessary), the subject will be closely monitored until the

toxicity is resolved to no worse than grade 2 severity (grade 1 if reported toxicity is initially grade 2) or is stabilized, at which point he/she will be removed from the study.

The Sponsor will provide written notification of all DLT determination decisions to the Investigator and DSMB members.

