Note: As stated in Section 5.2, certain transplant-related experiences will not be reported as serious adverse events unless the event is life threatening or fatal.

All adverse events will be graded for severity according to the NCI Common Terminology Criteria for Adverse Events (CTCAE), version 3.0 (available on line at http://ctep.cancer.gov/reporting/ctc.html).

Using the following criteria, Investigators also need to assess whether there is a reasonable possibility that study drug caused or contributed to the AE:

Yes (possibly, probably, or definitely related):

• There is a clinically plausible time sequence between onset of the AE and study drug administration

AND/OR

• There is a biologically plausible mechanism for study drug causing or contributing to the AE

No (unlikely, unrelated):

- Another cause of the AE is most plausible AND/OR
- A clinically plausible temporal sequence is inconsistent with the onset of the AE and study drug administration

AND/OR

• A causal relationship is considered biologically implausible

The Principal Investigator will be asked to list any other suspected causes.

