5.4.2 Adverse Events Requiring Expedited Reporting

All SAEs will be carefully monitored throughout the course of the study.

All SAEs, regardless of relationship to study drug, must be reported by the Investigator to XOMA or its designee within 24 hours of being notified of the event. The Investigator should contact XOMA or its designee by telephone, followed by a faxed initial SAE form. Additional written follow-up information, including a full description of the event and any sequelae, must follow as soon as available.

Telephone Report:

[name].	Office:	[contact]
Medical Monitor		[contact]

Concurrent SAE Form:

[name]	[contact]
	[contact]

For initial SAE reports, record all case details that can be gathered within 24 hours on the SAE Form. The completed SAE form should be faxed immediately upon completion. Relevant follow-up information should be submitted as soon as possible. All SAEs should also be reported to the IRB within the time frame determined by the institution at which the investigation is being carried out.

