6.5.1 Adverse Events

Treatment-emergent AEs reported during the study will be coded using the MedDRA dictionary. An AE will be summarized by dose group and the following:

- System organ class and preferred term
- System organ class and severity
- System organ class, preferred term and severity

These summaries will be presented for the following subsets:

- All adverse events
- Drug-related adverse events
- Adverse events resulting in discontinuation of study drug or the study
- Serious adverse events, including deaths
- Adverse events due to infectious and non-infectious regimen-related toxicities

For tables classifying AEs by severity, if a subject has multiple occurrences of an adverse event with the same MedDRA term, the most severe event will be chosen.

A summary and by-subject listing will be provided for any subject who died, experienced SAEs, or experienced AEs resulting in discontinuation of study drug or the study.

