6.5.2 Clinical Laboratory Evaluation

Laboratory values outside of the corresponding normal ranges will be identified and reported to the Sponsor.

The incidence of clinically significant abnormal changes in laboratory values compared with baseline (hematology, chemistry, and urinalysis), and the incidence of DLTs will be summarized by dose group (see Section 3.3.2 for the definition of DLT). MTD will have been exceeded if two or more subjects in a dose group experience a DLT. If, in the subsequent DSMB review of the data, no explanation for the serious adverse events other than use of study drug can be determined, the study may be stopped.

Changes from baseline in special studies parameters (which may include, but may not be limited to, LPS, LBP, BPI, soluble CD14, TLR4, membrane CD14, TNF-RI, IL-1, IL-6, IL-8, IL-10, IL-12 p70 and CRP) will be summarized by dose group.

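### The SAE reporting exemption for listed transplant events does not say whether it covers events judged related to opebacan, which leaves a gap in expedited reporting after the DLT window

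*Supplement*

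**What the plan says.** Section 5.2 introduces a list of adverse events and laboratory abnormalities "that are related to their transplant conditioning regimen or the transplant procedure". It includes nausea, severe mucositis, fever and neutropenia, opportunistic infection, VOD, renal insufficiency, transaminitis and GvHD. The rule follows: "These transplant-related experiences will not be reported as serious adverse events unless the event is life threatening or fatal". The next sentence reads: "However, they will be collected as AEs and noted as not related to the use of study drug where appropriate". The note in Section 5.1 repeats that "certain transplant-related experiences will not be reported as serious adverse events unless the event is life threatening or fatal".

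Section 5.1 also gives the seriousness criteria. Besides death and immediate threat to life, they include new or prolonged hospitalisation, disability and medically important events. The Investigator must rate seriousness, severity and relationship for every AE.

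Four other sections depend on how these events are classified:
- Section 3.3.2: "A DLT is defined as a toxicity of CTC grade 3 or greater severity". The event must also be judged related by the Investigator, occur within 4 weeks of administration, and be confirmed. Listed transplant events are not excluded.
- Section 5.4.2: "All SAEs, regardless of relationship to study drug, must be reported by the Investigator" within 24 hours.
- Section 6.5.1 tabulates by dose group a subset called "Serious adverse events, including deaths".
- Section 6.5.2 says that, after two or more DLTs in a group, the study may be stopped if "no explanation for the serious adverse events other than use of study drug can be determined".

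**The concern.** The exemption does not mention relationship to study drug. If it covers related events, one event can be a DLT and meet a seriousness criterion, yet not be reported as an SAE. Section 6.5.2 would then call serious adverse events what Section 5.2 had kept out of SAE reporting.

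Three things depend on SAE status: the 24-hour report to the sponsor, the SAE table by dose group, and the evaluation of serious events in Section 5.2 that can lead the DSMB to have the trial suspended. Safety is the first objective, and Section 3.2.2 says the drug has never been given to this population. Subjects are usually inpatients when dosed, so prolonged hospitalisation is the seriousness criterion most likely to apply. For listed terms it no longer triggers a report.

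**Working it through.** **1. The plan's own figure.** The only calculated figure near the DLT rule is Table 2 in Section 3.3.4, the probability that at most 1 of 6 subjects has a DLT: P(X ≤ 1) = (1 − p)^6 + 6p(1 − p)^5. At p = 0.10 this is 0.5314 + 0.3543 = 0.8857, as printed. All eight values reproduce to four decimals. The table does not depend on SAE status, so nothing in it changes.

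**2. Can a listed event be rated related?** Two places suggest that it can.
- Section 5.2 says listed events are noted as unrelated only where that is appropriate, which leaves room for some to be rated related.
- The relationship test in Section 5.1 asks whether the drug caused the event or contributed to it, and plausible timing can be enough. Transplant and drug can therefore both be causes. Section 5.1 also names fever and nausea as possible infusion effects, and both appear in the Section 5.2 list (fever together with neutropenia).

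**3. One event followed through the sections.** Take a grade 3 renal insufficiency, judged related, with onset inside 4 weeks, that prolongs the stay but does not threaten life.
- Section 5.1 criteria: serious.
- Section 3.3.2: a potential DLT, notified to the sponsor within 24 hours; a DLT once confirmed.
- Sections 5.1 (note) and 5.2, read as written: not reported as an SAE.
- Section 5.4.2: no 24-hour SAE report.
- Section 6.5.1: in the all-AE and drug-related subsets. If a confirmed DLT, also in the discontinuation subset and by-subject listing, because Section 3.3.2 stops study drug. Absent from the SAE subset if that subset is built from reported SAEs.
- Section 6.5.2: counted in DLT incidence.

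In a group of six, one such event would make the SAE table show 0/6 where the drug-related AE table shows 1/6 (17%). This is an illustration, not a forecast.

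**4. What has a 24-hour route inside the window?** Related events of grade 3 or more are covered as potential DLTs. Related grade 2 events may be reported as potential DLTs if the Investigator considers them a clinically significant concern, so that route exists but is discretionary.

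**5. What remains after the window?** Section 3.3.2 does not say whether 4 weeks runs from the start or the end of infusion. Dosing starts on Day −1 and ends on Day 2 (Groups 1–3), Day 6 (Group 4) or Day 13 (Group 5). Days left = 100 − (anchor day + 28).

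| Anchor | Window closes | Days left to Day 100 |
|---|---|---|
| Start, all groups (Day −1) | Day 27 | 73 |
| End, Groups 1–3 (Day 2) | Day 30 | 70 |
| End, Group 4 (Day 6) | Day 34 | 66 |
| End, Group 5 (Day 13) | Day 41 | 59 |

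Over those days a related listed event that is serious but not life threatening has no 24-hour route if the exemption is read broadly. Section 5.4.3 gives an immediate route, but only for fatal or life-threatening events attributed to the drug. Sections 5.0 and 7.4 ask for unexpected toxicity and significant events to be reported to the sponsor, but set no time limit. Under Section 4.3 and Appendix 1, the Day 35, 42 and 49 assessments are for inpatients only. For a subject discharged before then, the next scheduled AE collection after Day 28 may be Day 100, unless aGvHD of grade 2 or more triggers a visit.

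**The case against.** The best defence is the wording of the list. It is introduced as events caused by conditioning or transplant, and the exemption applies to transplant-related experiences. On that reading an event attributed to opebacan was never exempt. This is a reasonable reading and may be what the sponsor intended. It does not settle the case where both causes are plausible, which Sections 5.1 and 5.2 both allow for, and no sentence states it.

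The second defence is that Section 5.2 governs reporting, not tabulation. Seriousness is rated for every AE, and Section 6.5.1 does not confine its SAE subset to expedited reports. This stands: absence from the SAE table is possible, not certain.

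Third, the phrase in Section 6.5.2 may be loose wording. That is fair. It is evidence of inconsistency, not proof that every DLT must be an SAE.

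A reader might go further and infer that related serious events disappear from the safety evaluation, or that escalation could proceed on an undercount. The documents do not support either. Confirmed DLTs reach the sponsor and appear in several outputs. Under Section 3.3.4 escalation rests on DLT counts and on DSMB review of all available safety information, not on the SAE table. A reader might also infer that related grade 2 events have no expedited route at all; Section 3.3.2 gives a discretionary one within the 4 weeks.

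**Conclusion.** The point holds as an inconsistency in classification and reporting. Sections 5.1 and 5.2 do not say whether the exemption covers listed events judged related to opebacan. On the broad reading, a DLT can fall outside 24-hour SAE reporting and possibly outside the SAE subset. The practical gap is expedited reporting of related, serious, non-life-threatening listed events for about 59 to 73 days before Day 100. That range takes 4 weeks as 28 days and Day 100 at its nominal date; the ± 14-day visit window would move it. It also assumes that sites apply the exemption without regard to relationship. Table 2, the DLT count and the escalation rule are unaffected. This is an inexpensive improvement, not a flaw that threatens the trial's conclusions.

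**What to change.** Reconcile Sections 5.1 and 5.2 with Sections 3.3.2, 5.4.2, 6.5.1 and 6.5.2. In 5.1 and 5.2, limit the reporting exemption to listed events that the Investigator judges not related to opebacan, so that related listed events meeting a Section 5.1 criterion follow Section 5.4.2. In 6.5.1, state that the SAE subset is built from the Investigator's seriousness rating, whether or not an expedited report was filed. In 6.5.2, say whether the events under review are DLTs, SAEs or both.

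No new data are needed, because seriousness and relationship are already rated for every AE. No dose, treatment or escalation rule changes. The cost is a few sentences in the protocol, matching instructions to sites, and a few extra SAE forms.

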5.3 Laboratory Tests/Other Evaluations

This study involves various procedures and tests performed repeatedly throughout the study. If a subject has a clinically significant abnormal laboratory test value that is not an expected

result of study drug administration or was not present at baseline, the test will be repeated and the subject will be followed until the test value has returned to the normal range or the Investigator has determined that the abnormality is chronic or stable.

The Investigators are required to evaluate all abnormal laboratory results for their clinical significance. An isolated abnormal laboratory result in the absence of any associated clinical finding may not be considered an AE. An abnormal laboratory result will be considered clinically significant and recorded as an AE when it is part of a clinical abnormality requiring specific medical intervention or follow-up.

A complete physical examination will be performed at prescreening, Day 28, Day 100 and hospital discharge. Vital signs will be recorded at specified time points throughout the study. Vital sign measurements consist of blood pressure, pulse rate, body temperature and body weight.

For women of child-bearing potential, a urine or serum pregnancy test will be performed at screening.

5.4 Procedures for Eliciting, Recording, and Reporting Adverse Events

Adverse events may be directly observed or elicited by the Investigator using open-ended or directed questions, and/or volunteered by the subjects.

5.4.1 Recording Adverse Events

To improve the quality and precision of acquired AE data, Investigators should observe the following guidelines:

- Whenever possible, use recognized medical terms when recording AEs on the AE pages of the CRF. Do not use colloquialisms and/or abbreviations.
- If known, record the diagnosis (i.e., disease or syndrome) rather than component signs and symptoms on the AE pages of the CRF (e.g., record congestive heart failure rather than dyspnea, rales, and cyanosis). However, signs and symptoms that are considered unrelated to an encountered syndrome or disease should be recorded as individual AEs on the CRF (e.g., if congestive heart failure has not been documented, each symptom in the above example would be recorded as a separate AE).
- Adverse events occurring secondary to other events (e.g., sequelae) should be identified by the primary cause. A "primary" AE, if clearly identifiable, generally represents the most accurate clinical term to record on AE pages of the CRF. Events occurring secondary to the primary event should be described in the narrative description of the case. For example:

Orthostatic \rightarrow Fainting and \rightarrow Head \rightarrow Neck pain hypotension fall to floor trauma

The primary AE in this example is orthostatic hypotension.

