5.1 Adverse Events

The occurrence of an adverse event will be determined based on observed or volunteered signs and symptoms, as well as changes in the subject's physical examination and laboratory results.

Adverse events that occur during the study will be recorded on the appropriate AE pages of the CRF. On Day -1, a "signs and symptoms inventory" CRF page will be completed prior to initial dosing with opebacan.

An AE is defined as any untoward medical occurrence (e.g., sign, symptom, disease, syndrome, intercurrent illness, abnormal laboratory finding) that emerges or worsens relative to pretreatment baseline during the study, regardless of the suspected cause. Untoward medical events that occur from the time the subject signs the informed consent form to the time the administration of the drug starts are not considered adverse events, and should be recorded under medical history.

Acute infusional adverse events may include headache, fever, chills, myalgia or nausea experienced 12 to 48 hours following initiation of IV administration of study drug.

All AEs will be evaluated by the Investigator for their seriousness, severity, relationship to study drug, and outcome.

An AE occurring at any dose (including overdose) should be classified as **SERIOUS** if:

- It resulted in death (i.e., the AE caused or led to death).
- It was life threatening (i.e., the AE placed the subject at immediate risk of death; an AE should not be classified as life-threatening if it hypothetically might have caused death if it were more severe).
- It required or prolonged inpatient hospitalization (i.e., the AE required at least a 24-hour inpatient hospitalization or prolonged a hospitalization beyond the expected length of stay; hospitalizations for elective medical/surgical procedures, scheduled treatments, or routine check-ups are not SAEs by this criterion).
- It was disabling (i.e., the AE resulted in a substantial disruption of the subject's ability to carry out normal life functions).
- It resulted in a congenital anomaly/birth defect (i.e., an adverse outcome in a child or fetus of a subject exposed to the molecule or study drug prior to conception or during pregnancy).
- It does not meet any of the above criteria for a serious AE but may jeopardize the subject or may require medical or surgical intervention to prevent one of the outcomes listed above

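### Section 5.4.1 generally leaves secondary events to the narrative, so a non-fatal grade 3–4 sequela of a milder event can be missing from the severity tables by dose group

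*Supplement*

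**What the plan says.** Protocol section 5.4.1 (Recording Adverse Events) gives sites guidelines for the AE pages of the CRF. Where one event leads to others, it says: "A 'primary' AE, if clearly identifiable, generally represents the most accurate clinical term to record on AE pages of the CRF". For the later events it says: "Events occurring secondary to the primary event should be described in the narrative description of the case". It illustrates this with a chain of four events: orthostatic hypotension, a faint and fall, head trauma and neck pain. It concludes: "The primary AE in this example is orthostatic hypotension". Severe or serious later events are not treated differently.

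Section 5.1 (Adverse Events) is broader. It counts any untoward occurrence that emerges or worsens after baseline as an adverse event, whatever the cause, and says: "Adverse events that occur during the study will be recorded on the appropriate AE pages of the CRF". On severity it says: "All adverse events will be graded for severity according to the NCI Common Terminology Criteria for Adverse Events (CTCAE), version 3.0".

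Section 6.5.1 codes treatment-emergent events with MedDRA and summarises them by dose group, among other ways by "System organ class, preferred term and severity". If a subject has several occurrences of the same MedDRA term, the most severe one is used.

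Section 3.3.2 defines a dose-limiting toxicity (DLT) as a related, confirmed toxicity of grade 3 or greater within four weeks of administration. Sites must notify the sponsor of a potential DLT within 24 hours.

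**The concern.** The first objective of the trial is safety, and the results are purely descriptive, so the adverse event tables by dose group are a main product. Their content depends on which events receive an AE line. Under 5.4.1 a severe event that follows a milder one may appear only as free text attached to the milder event. The tables would then show the milder grade, in the organ class of the first event. They would be silent on the severe grade and on the second organ system. In a transplant population where one complication can lead to another, this would understate worst severity and organ involvement. Sites could also differ in how they apply the rule, because 5.1 tells them to record and grade all adverse events.

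**Working it through.** The plan gives no figure on this point, so the check is a comparison of the sections, followed by the size of one omission.

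1. **Recording.** Section 5.4.1 itself calls the later events adverse events that are secondary to others. Section 5.1 sends adverse events to the AE pages and has all of them graded. Section 5.4.1 sends the later ones to the narrative. A site cannot do both for the same event, and no sentence says which section prevails.

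2. **Strength of the rule.** It applies when the primary event is clearly identifiable, and it is qualified by the word generally. It is therefore not an absolute instruction to record only the first event. These qualifiers leave discretion to the site; they do not exempt a grade 3–4 sequela.

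3. **The protocol's own example.** Four events are named and one becomes the primary AE, so 4 − 1 = 3 of 4 go to the narrative. The example gives no grades. It shows the mechanism, not how often a severe event would be lost.

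4. **Whether the tables can recover the event.** Take a grade 2 primary event with a grade 3 sequela in another organ class (a hypothetical case).
   - Following 5.1: two AE lines, one at grade 2 in the first class and one at grade 3 in the second.
   - Following 5.4.1: one AE line, at grade 2 in the first class.
   - The worst-grade rule in 6.5.1 works only among occurrences of the same MedDRA term, so it does not link the two events. No rule in the documents gives the primary event the grade of its worst consequence. The grade 3 event is absent from the table.

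5. **Other routes by which the event might be captured.**
   - Death: 5.4.3 requires the event that resulted in death to be on the AE CRF. Fatal sequelae are covered, so the gap concerns non-fatal ones.
   - Serious events: 5.4.2 asks SAE follow-up to describe sequelae. That is report text, and 6.5.1 does not say that it is coded. Section 5.2 also exempts many transplant-related events from SAE reporting unless life-threatening or fatal. For those, the AE line is the main coded record.
   - Transplant complications: 6.4 describes them by subject and summarises them only if there are enough cases.
   - Laboratory abnormalities: 6.5.2 summarises clinically significant changes by dose group, whatever the AE coding. This covers part of the gap.

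6. **Size of one omission.** Each dose group has 6 subjects. If the tables show proportions of subjects, one subject whose only grade 3 event of that kind is left in the narrative changes a cell from 1/6 = 16.7% to 0/6 = 0%. In a group expanded to 12 after a graft failure, the change is 1/12 = 8.3%. The number of such subjects cannot be derived from the documents.

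**The case against.** The strongest objection concerns dose escalation. A reader might infer that a narrative-only sequela also drops out of the DLT count, so that the chance of escalating is higher than Table 2 states. The documents do not support this. Section 3.3.2 defines a DLT on the toxicity itself, not on a primary term or a CRF line. It has its own 24-hour notification, and confirmation by the investigator and sponsor or by the DSMB. Sections 3.1 and 3.3.4 base escalation on DSMB review of all available safety information, and 6.5.2 summarises DLTs separately. Any revised escalation probability would need a share of DLTs missed, which the documents do not give. If 3.3.2 is followed, that share is zero and Table 2 stands; its eight values reproduce as exact binomial probabilities for six subjects. This objection holds. Only an ambiguity remains. The sentence on stopping study drug begins "If it is determined that an AE meets all of the criteria for DLT", and 5.4.1 does not say that a sequela described only in the narrative is still assessed for DLT.

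A second objection is that primary-cause recording is an accepted convention, stated here as a guideline to improve data quality, and that it keeps one episode from being counted several times. That is a good reason to keep it for minor sequelae, but not for leaving a grade 3–4 event ungraded and uncoded.

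A third is that section 4.2 refers to separate CRF Completion Guidelines, which are not among the documents and may already split out severe sequelae. That is possible. The protocol would still contradict itself, and a short addition would settle it.

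A fourth is that 5.2 says transplant-related events will be collected as adverse events, and that schedule-driven measures such as LVEF, cardiac serology and aGvHD grade do not depend on AE recording. This narrows the practical effect but does not reconcile 5.4.1 with 5.1.

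**Conclusion.** The point holds for the safety tables. As written, 5.4.1 conflicts with 5.1, and a non-fatal grade 3–4 sequela of a milder primary event can be missing from the 6.5.1 severity and organ-class tables by dose group. Any such loss understates severity, and each affected subject counts for one in six in an unexpanded group. The conclusion assumes that sites follow 5.4.1 as written, that narrative text is not coded, and that the CRF guidelines do not already make an exception. How often it would happen is unknown.

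It does not extend to dose escalation: an under-count of DLTs is not shown, and Table 2 is not called into question. It would also be too strong to say that only the first event of any chain is ever recorded, given the qualifiers in 5.4.1 and the separate rule for fatal events. The change is worth making because safety is the first objective and the correction is small.

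**What to change.** Keep the primary-cause rule for minor sequelae and add three statements to section 5.4.1:

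- A secondary event that is CTCAE grade 3 or higher, or serious, is recorded as its own AE line, graded, assessed for relatedness and linked to the primary event.
- The 6.5.1 tables include these lines.
- Section 5.4.1 does not limit DLT assessment under section 3.3.2.

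The CRF Completion Guidelines should carry the same wording.

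The cost is a short paragraph, a link field on the AE page and a few more AE lines. The drawback is that one chain of events may appear under several preferred terms; the link field lets it be read as one episode. No dose, stopping rule or DLT criterion changes.
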